## 5.6 Criteria for Halting the Study

If there are  $\geq 2$  treatment-related Grade 4 non-hematologic events in the first 10 patients or any grade 5 events, enrollment in the study will be temporarily halted pending review by the PI and the study sponsors regarding the need for modifications to the protocol or consent.

## 6. DOSING DELAYS/DOSE MODIFICATIONS

### 6.1 Dose Modifications due to Toxicity

Because this study assesses the benefits of treating early-stage, asymptomatic CLL/SLL patients who would not otherwise be receiving therapy, the definition of “unacceptable” toxicity will be defined as any treatment-related Grade 4 non-hematologic toxicity or any treatment-related Grade  $\geq 3$  toxicity deemed unmanageable or unacceptable by the patient, his or her treating physician, or the study chair. As described, in [Section 5.3](#) and [Section 5.5](#), unacceptable toxicity will require discontinuation of protocol therapy.

Subjects will be evaluated for adverse events at each visit with the NCI CTEP CTCAE version 5 used as a guide for grading of severity for both hematologic and non-hematologic toxicity.

### 6.2 Criteria for Starting a New Cycle

A new course of treatment may begin on the scheduled day 1 of a new cycle if:

- All lenalidomide-related hematologic toxicity has resolved to Grade  $\leq 1$  severity.
- Any lenalidomide-related rash or neuropathy that may have occurred has resolved to Grade  $\leq 1$  severity.
- Any other drug-related adverse events that may have occurred have resolved to Grade  $\leq 1$  severity.

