### 5.1.1 Lenalidomide

Lenalidomide treatment will be administered on a continuous basis. However, for convenience of dose-modification, response, and toxicity monitoring, the treatment period will be divided into cycles of 28-day length. Lenalidomide will be dispensed in no more than one 28-day supply. Before each supply is released, each patient's medication calendar from the previous cycle will be reviewed to assess compliance. Patients will also be required to review the Lenalidomide Information Sheet ([Appendix E](#)) and the Education and Counseling Guidance Documents ([Appendix D](#)) prior to receiving each monthly supply of lenalidomide.

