### 5.3 Duration of Therapy

Patients demonstrating clinical benefit, defined as achievement of an objective response (CR, CRi, or PR) or stable disease (SD), may continue therapy for up to 24 cycles (approximately 2 years) of treatment with lenalidomide. Therapy beyond 24 cycles may be considered after discussion with the principal investigator and consultation with the study sponsor.

Investigators are encouraged to keep patients experiencing clinical benefit on study unless significant toxicity puts the subject at risk or routine noncompliance puts the study outcomes at risk. If the subject meets any 1 of the following criteria, withdrawal from treatment is mandatory:

- Disease progression meeting 2008 IWCLL consensus criteria for treatment.
- Intercurrent illness that prevents further lenalidomide administration.
- Any treatment-related Grade 4 non-hematologic toxicity.
- Unacceptable and/or unmanageable Grade  $\geq 3$  toxicity attributable to lenalidomide.
- Any treatment-related hematologic or non-hematologic toxicity delaying treatment more than 14 days.

- Development of autoimmune hemolytic anemia (AIHA) or immune-mediated thrombocytopenia (ITP)
- Subject elects to withdraw from study or becomes pregnant.
- General or specific changes in the patient's condition rendering the patient unacceptable for further treatment in the judgment of the investigator.
- Subject is noncompliant with study procedures and/or scheduled evaluations.
- Investigator considers withdrawal to be in the best interest of the subject.
- Diagnosis of new or secondary malignancies after initiating treatment

Subjects with inadequate study drug compliance (i.e.  $\leq$  80% of planned doses administered) may be replaced.

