### 6.3.1 Hematologic Toxicity

- In the instance of Grade  $\geq 3$  lenalidomide-related hematologic toxicity on day 1 of a cycle, delay lenalidomide therapy and monitor CBC at least weekly. If toxicity resolves to Grade  $\leq 1$  within 2 weeks, then resume lenalidomide at the next lower dose level.
- If Grade  $\geq 3$  lenalidomide-related hematologic toxicity occurs during a cycle, delay lenalidomide therapy and monitor CBC at least weekly. If toxicity resolves to Grade  $\leq 1$  within 2 weeks, then resume lenalidomide at the next lower dose level.
- If treatment is delayed for more than 2 weeks, discontinue protocol therapy.
- WBC colony stimulating factors may not be used to avoid dose reductions but can be used in the treatment of febrile neutropenia as outlined in 6.3.2 below.
- Because of the potential to increase the risk for venous thromboembolic disease, the use of erythropoietic stimulating agents (ESAs) will not be permitted.
- Because a decrease in absolute lymphocyte count (and thus WBC count) is an expected therapeutic outcome of treatment with Lenalidomide, no dose modification is required for the AEs of White Blood Cell Decreased or Lymphocyte Count Decreased.

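### Section 6.3.1 exempts lymphocyte and white-cell decreases from dose modification, but the cycle-start, escalation, 14-day and Grade 4 rules still act on them

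*Combined protocol and SAP*

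**What the plan says.** Five places in the protocol govern what happens when a blood count falls on lenalidomide.

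- **6.3.1 (hematologic toxicity).** At Grade 3 or higher the instruction for "lenalidomide-related hematologic toxicity on day 1 of a cycle, delay lenalidomide therapy and monitor CBC at least weekly" applies. The drug resumes one dose level lower if the toxicity returns to Grade 1 or lower within 2 weeks. Otherwise: "If treatment is delayed for more than 2 weeks, discontinue protocol therapy". The last bullet covers lymphocyte and white-cell decreases. It says that such a fall "is an expected therapeutic outcome of treatment with Lenalidomide" and that "no dose modification is required for the AEs of White Blood Cell Decreased or Lymphocyte Count Decreased".
- **6.2 (starting a new cycle).** The first criterion is that "All lenalidomide-related hematologic toxicity has resolved to Grade" 1 or lower. The third is "Any other drug-related adverse events that may have occurred have resolved to Grade" 1 or lower. No event is exempted.
- **5.1.1 and 6.4 (escalation to 5 mg/day).** Hematologic toxicity must be at Grade 1 or lower on Day 1, and so must other drug-related events. In 5.1.1 the hematologic item is not limited to drug-related toxicity; in 6.4 it is. Neither exempts the two events.
- **5.3 (mandatory withdrawal).** The list includes "Any treatment-related hematologic or non-hematologic toxicity delaying treatment more than 14 days", with no minimum grade and no exemption.
- **5.5 (removal).** Any Grade 4 toxicity attributed to lenalidomide requires discontinuation, again without exemption.

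The Summary of Changes lists the exemption against 6.3.1 only.

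**The concern.** The protocol calls a falling lymphocyte count an intended effect and excuses it in one section, yet leaves it as a reason to hold, not escalate or withdraw in others. No order of precedence is stated. One investigator could rely on 6.3.1 and continue. Another could rely on 6.2, hold, and then have to withdraw the patient under 5.3. Both would be following the text.

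What is at stake is consistent handling of patients still on lenalidomide, and a clean record of why treatment stopped. Section 13.5 plans to summarize reasons for discontinuation and to analyze time to treatment failure, which runs from study entry to discontinuation of treatment. A withdrawal that follows from which section was read enters both summaries.

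**Working it through.** No sample size, power or error-rate figure is involved, so the check sets the rules side by side for a lenalidomide-related event present on Day 1 of a new cycle.

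| Day 1 finding | 6.2 | 6.3.1 | Escalation (5.1.1, 6.4) | 5.3 | 5.5, Grade 4 rule |
|---|---|---|---|---|---|
| Lymphocyte or white-cell decrease, Grade 1 | cycle may begin | no modification | not blocked | not engaged | not engaged |
| Same, Grade 2 or 3 | cycle not begun | no modification | blocked at that visit | withdrawal if delay exceeds 14 days | not engaged |
| Same, Grade 4 | cycle not begun | no modification | blocked at that visit | withdrawal if delay exceeds 14 days | discontinue |
| Other count, Grade 2 | cycle not begun | silent | blocked at that visit | withdrawal if delay exceeds 14 days | not engaged |
| Other count, Grade 3 | cycle not begun | delay, then one level lower | blocked at that visit | withdrawal if delay exceeds 14 days | not engaged |

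**Rows 2 and 3** hold the conflict: 6.3.1 asks for no change while the other sections hold or stop the drug.

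**Row 4** is a gap. Section 6.2 creates a delay at Grade 2, and 6.3.1 does not say at what dose level treatment resumes afterwards.

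**Row 5** is consistent between 6.2 and 6.3.1.

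**Does the exemption reach 6.2 if the fall is treated as an effect and not as toxicity?** No. Section 6.3.1 itself calls these events AEs, and the third criterion of 6.2 covers any other drug-related AE above Grade 1.

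**How withdrawal arises.** Section 6.2 only holds a cycle. Withdrawal needs a further step: the decrease stays above Grade 1, the delay passes 14 days, and 5.3 applies. The 2-week limit in 6.3.1 is the same length (2 × 7 = 14 days).

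**How often the gate is met.** Over the 24 lenalidomide cycles allowed by 5.3 there are 24 − 1 = 23 new-cycle starts after the first. More follow if treatment is extended, which 5.3 permits after discussion.

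**How many patients.** This cannot be computed. The adverse event list in 7.1 places both events in its column for 20% or less, but that figure is not specific to Grade 2 or higher or to this population.

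**The case against.** The strongest reply is that the exemption already covers holds. The introduction to 6.3 says the section sets criteria for holding as well as modifying the dose, and 6.1 uses dose modification broadly enough to take in discontinuation. The exemption also sits among bullets whose instruction is to delay. On that reading no delay occurs and the 14-day clock in 5.3 never starts. This is arguable within 6.3. It does not clearly reach 6.2, which is a separate section, or 5.3 and 5.5. The heading of section 6 also names delays apart from modifications.

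A second reply is that the Grade 2 limit in 6.2 and the Grade 3 limit in 6.3.1 do not contradict each other for other counts: Grade 2 waits, Grade 3 waits and reduces. That stands. Section 5.1.1 says that "Lenalidomide treatment will be administered on a continuous basis" but also that cycles serve dose modification, response and toxicity monitoring, so a check at the cycle boundary is intended. Only the unstated resumption level remains.

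A reader might infer more, and the documents do not support it:

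- **That a hold would separate vaccine from drug in Arm A.** Section 5.1.2 ties PCV13 to Day 1 of Cycles 3 and 5, and the example after Table 4 shows that held days do not advance the cycle day. The vaccine would most naturally move with the delayed cycle; at most the 8-week interval lengthens.
- **That the CR endpoint is compromised.** The exemption is new in this amendment, and section 9 says that study endpoints are met and few patients remain on treatment.
- **That any responding patient is stopped.** Only a decrease of Grade 2 or higher triggers the gate. Section 11.2 asks for lymphocytes below 5,000/µL for CR, and the documents give no grade cut-offs showing that a response reaches Grade 2.
- **That escalation is lost for good.** Sections 5.1.1 and 6.4 allow re-evaluation at later cycles.

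**Conclusion.** The inconsistency is real and can be read directly from the text. A lenalidomide-related lymphocyte or white-cell decrease of Grade 2 or higher on Day 1 needs no dose modification under 6.3.1. The same decrease blocks the cycle under 6.2, blocks escalation at that visit, and ends treatment under 5.3 if the delay exceeds 14 days. At Grade 4, section 5.5 ends treatment as well.

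Its practical size is small and cannot be put as a number. It concerns patients still on treatment under the current version, and no effect on vaccine timing, the primary endpoint or the CR endpoint is demonstrated. The conclusion assumes that the decrease is attributed to lenalidomide and that each section is applied as worded. If the amendment meant the exemption to hold throughout, the other sections do not yet say so.

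**What to change.** At the next amendment, reconcile 5.1.1, 5.3, 5.5, 6.2 and 6.4 with 6.3.1, so that all six state the same handling of White Blood Cell Decreased and Lymphocyte Count Decreased for starting a cycle, escalation, the 14-day rule and the Grade 4 rule. State also how a Grade 2 hematologic delay under 6.2 relates to 6.3.1, including the dose level at resumption. Which rule and which threshold apply is for the sponsor to decide; none is proposed here.

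The cost is a few words in each section. Blood counts are already scheduled, so no new assessment or data item is needed.

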### 6.3 Criteria for Dose Reductions

Dose modifications of lenalidomide may be made at any time during treatment if lenalidomide is held for toxicity or at the start of a new cycle if the previous dose was not well-tolerated. Lenalidomide dose levels are displayed in [Table 4](#). No dose reductions below dose level -1 (2.5 mg every other day) will be permitted. Specific criteria for holding and/or modifying the dose of lenalidomide are further detailed in this section.

**Table 4. Lenalidomide Dose Levels**

Dose Level	Lenalidomide Dose
1	5 mg daily
0	2.5 mg daily
-1	2.5 mg every other day

If a toxicity requiring dose reduction is experienced, appropriate measures will be taken as described below (6.3.1), and when therapy with the study drug resumes it will be considered the next day of the patient's current cycle. For example, if drug is held prior to the daily dose on day 8 for a toxicity, and the toxicity resolves to allow lenalidomide resumption after 7 days, it would then be considered day 8 of the current cycle.

### 6.3.1 Hematologic Toxicity

- In the instance of Grade  $\geq 3$  lenalidomide-related hematologic toxicity on day 1 of a cycle, delay lenalidomide therapy and monitor CBC at least weekly. If toxicity resolves to Grade  $\leq 1$  within 2 weeks, then resume lenalidomide at the next lower dose level.
- If Grade  $\geq 3$  lenalidomide-related hematologic toxicity occurs during a cycle, delay lenalidomide therapy and monitor CBC at least weekly. If toxicity resolves to Grade  $\leq 1$  within 2 weeks, then resume lenalidomide at the next lower dose level.
- If treatment is delayed for more than 2 weeks, discontinue protocol therapy.
- WBC colony stimulating factors may not be used to avoid dose reductions but can be used in the treatment of febrile neutropenia as outlined in 6.3.2 below.
- Because of the potential to increase the risk for venous thromboembolic disease, the use of erythropoietic stimulating agents (ESAs) will not be permitted.
- Because a decrease in absolute lymphocyte count (and thus WBC count) is an expected therapeutic outcome of treatment with Lenalidomide, no dose modification is required for the AEs of White Blood Cell Decreased or Lymphocyte Count Decreased.

### 6.3.2 Febrile Neutropenia

- In the event of febrile neutropenia occurring at any time during a cycle, hold lenalidomide therapy and administer G-CSF until recovery (ANC  $\geq 1500/\mu\text{L}$  + absence of fever). If the patient recovers within 2 weeks, then resume lenalidomide at the next lower dose level.
- If treatment is delayed for more than 2 weeks, discontinue protocol therapy

### 6.3.3 Allergic Reaction

- Patients experiencing an IgE-mediated allergic reaction (including anaphylaxis, hives, or asthma) attributable to lenalidomide should discontinue treatment immediately and be removed from further protocol therapy.
- In the instance of any other Grade 2 allergic reaction attributable to lenalidomide, hold lenalidomide therapy and monitor toxicity at least weekly. If toxicity resolves to Grade  $\leq 1$  within 2 weeks, then resume lenalidomide at the next lower dose level.
- In the instance of any Grade  $\geq 3$  allergic reaction to lenalidomide, remove patient from protocol therapy.
- For any Grade  $\geq 3$  allergic reaction to Prevnar 13 vaccine, further vaccination must be discontinued. Further treatment with lenalidomide, however, can be continued.

### 6.3.4 Dermatologic and Skin Toxicity

- For any grade bullous, hemorrhagic, or desquamating rash (i.e. TEN), remove patient from protocol therapy.
- For any grade erythema multiforme, remove patient from protocol therapy.
- For other Grade  $\geq 3$  non-desquamating rash, hold lenalidomide therapy and monitor toxicity at least weekly. If toxicity resolves to Grade  $\leq 1$  within 2 weeks, then resume lenalidomide at the next lower dose level.

### 6.3.5 Autoimmune Hemolytic Anemia or Thrombocytopenic Purpura

Lenalidomide will be discontinued in patients developing autoimmune hemolytic anemia or autoimmune thrombocytopenia.

### 6.3.6 Cardiac Toxicity

- For lenalidomide-related grade 2 toxicity, hold lenalidomide and follow at least weekly. If toxicity resolves to Grade  $\leq 1$  within 2 weeks, then resume lenalidomide at the next lower dose level.
- For lenalidomide-related Grade  $\geq 3$  toxicity, discontinue lenalidomide.

### 6.3.7 Venous Thromboembolic Disease

For any grade deep venous thrombosis, arterial thrombosis, or embolism, discontinue lenalidomide.

### 6.3.8 Tumor Flare

- Swelling, erythema, and tenderness of lymph nodes (especially pathologically involved lymph nodes) are expected effects of treatment with lenalidomide. First line treatment is analgesics (e.g. NSAIDs, acetaminophen, oral narcotics) or corticosteroid therapy at the discretion of the treating physician. Suggested corticosteroid dosing is detailed in **5.2.1** above.
- Symptomatic tumor flare alone will not require that lenalidomide be held unless:
  - Symptomatic tumor flare persists beyond 3 days of corticosteroid treatment
  - Treating physician believes it is in the patient's best interest.
- If lenalidomide is held, therapy should be resumed when tumor flare resolves, or at the principal investigator's discretion.

### 6.3.9 Tumor Lysis Syndrome (NCI CTCAE Grade > 2)

- Hold (interrupt) lenalidomide dose.
- First episode: When attributable electrolyte abnormalities resolve to Grade  $\leq 1$ , restart lenalidomide at the current dose with appropriate TLS prophylaxis. .
- Subsequent episodes at the same dose level: When attributable electrolyte abnormalities resolve to Grade  $\leq 1$ , restart lenalidomide at the next lowest dose level with appropriate TLS prophylaxis.
- Subjects should be closely monitored for signs of TLS after resuming treatment. To monitor for TLS, serum chemistry and uric acid tests should be performed on Day 3 or Day 4 following re-initiation of lenalidomide and at least every week following re-initiation of lenalidomide for 4 consecutive weeks.

### 6.3.10 Infection

It is imperative that accurate reporting of infectious events occur not only as a secondary endpoint of the study, but also so prophylactic therapies (if needed) can be included for future patients enrolled. Infectious toxicity (particularly Grade  $\geq 2$  severity) needs to be recorded and graded in a standard fashion both during treatment and at least every three months following completion of protocol therapy for patients remaining on study. The following information related to all infections must be documented: site of infection (lungs, sinus, skin, blood, urine, fever of unknown origin, etc.), causative agent (type of bacteria, fungus, virus, etc.) if any identified, specific therapeutic interventions. All herpes simplex and varicella zoster cases should be reported and noted as infectious (not skin) toxicities.

- Because infections are an expected complication of CLL, infections occurring in the absence of hematologic toxicity (i.e those not meeting criteria for neutropenic fever) will not require dose reductions.
- For Grade  $\geq 3$  infection, hold lenalidomide and administer medically appropriate therapy. If toxicity resolves to Grade  $\leq 2$  within 2 weeks, then resume lenalidomide at the same dose level.
- Lenalidomide therapy can continue during an episode of Grade  $\leq 2$  infection, so long as infection is adequately controlled.

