#### 5.4 Duration of Follow Up

Each subject should be followed for at least 30 ( $\pm 7$ ) days after his or her last dose of lenalidomide (i.e. the “safety follow-up period”) to monitor for resolution or progression of AEs and to document the occurrence of new events unless the subject receives a new CLL therapy within this time frame.

Subjects who withdraw consent should still be encouraged to complete the safety follow-up assessments, but these assessments cannot be mandated once consent is withdrawn. Patients removed from study for unacceptable adverse events will be followed until resolution or stabilization of the adverse event.

Beyond the safety follow-up period, patients no longer receiving protocol therapy will continue to be evaluated at 3 month intervals for the first year and every 6 months thereafter until they receive a new CLL therapy, withdraw consent, or expire. Patients may remain in follow-up if disease progression occurs. Required historical, laboratory, and physical examination procedures at each follow-up visit are detailed in the **Study Table** ([Section 10](#)).

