## 10. STUDY CALENDAR

Screening evaluations including history and physical examination and all laboratory studies are to be conducted within 14 days prior to the start of protocol therapy. CT scans of the chest, abdomen and pelvis will be completed within 6 weeks and bone marrow biopsy and aspirate (optional) are to be completed within 12 weeks prior to the start of therapy and should include evaluation for myelodysplasia. Visits Cycle 7+ have a +/- 7 day visit window. Follow-Up visits have a +/- 14 day visit window. Additional required data are summarized in the study calendar.

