### Schedule of Study Assessments: Arm B (Sequential)

Procedure	Screening	Cycle 1	Cycle 2	Cycle 3	Cycle 4 & 5				Cycle 6	Cycle 7+	End of Therapy o	Follow-Up p
					W1	W2	W3	W4				
Clinical Assessment												
Informed Consent	X											
Physical Examination a	X	X	X	X	X	X	X	X	X	X	X	
ECOG Performance Status b	X	X	X	X	X	X	X	X	X	X	X	
Concomitant medications	X	X	X	X	X	X	X	X	X	X	X	
Interval infection history c		X	X	X	X	X	X	X	X	X	X	
Record adverse events		X	X	X	X	X	X	X	X	X	X	
Perform Drug Accountability d	X				X	X	X	X	X	X	X	
Education and Counseling e					X				X	X	X	
Response assessment n					C5					X n	X	X
Laboaratory Studies and Procedures												
ECG	X											
Complete blood count m	X	X	X	X	X	X	X	X	X	X	X	X
Serum chemistries f	X	X	X	X	X	X	X	X	X	X	X	
Urinalysis	X											
Quantitative immunoglobulins	X	X		X	X					Every 6 mo	X g	X
Direct and indirect antiglobulin test	X											
TSH	X										X	
Pregnancy testing g	X				X g	X	X	X	X	X	X	
Bone marrow biopsy h	Optional										X	
Risk stratification studies i	X											
CT scans r	X										X	
Anti-pneumococcal antibody titers		X		X	X							
Treatment												
Allopurinol l					X	X	X	X				
Thromboprophylaxis k					X	X	X	X	X	X		
Dispense Lenalidomide l					X	X	X	X	X	X		
Lenalidomide					X	X	X	X	X	X		
PCV13 administration		X		X								
Correlative Studies												
Pharmacokinetic Studies s					C5 D1,2							
Pharmacodynamic Studies t	X	X			C4 D1,3 C5 D1	C4 D8			X			

- a. Physical examination should include vitals signs, weight, general physical examination (including neurologic examination), measurement of liver and spleen span in centimeters below the costal margin in the anterior axillary line, and bi-dimensional measurement of cervical, supraclavicular, axillary, and inguinal nodes.
- b. See [Appendix A](#).
- c. See [6.3.10](#) for required information to be documented for each episode of infection.
- d. Patient medication diary is reviewed to assess patient compliance on the first day of each cycle in which lenalidomide is administered.

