- i. Risk stratification studies will include serum  $\beta$ 2-microglobulin in addition to tests performed on the screening bone marrow biopsy specimen: IgVH mutational analysis (unless already known), interphase cytogenetics, stimulated karyotype and standard CLL FISH panel.
- j. Allopurinol should be administered beginning 3 days before first lenalidomide administration and continued through the first cycle of lenalidomide treatment in its entirety. Allopurinol can be continued during subsequent cycles at the treating physician's discretion.
- k. Thromboprophylaxis should begin with lenalidomide in patients at high-risk for venous or arterial thromboembolism (see [5.2.3](#)).
- l. Only enough lenalidomide for 28 days or one cycle of study treatment (whichever is shorter) may be provided to the patient each cycle.
- m. CBC is checked on D1 and D8 during the first cycle of lenalidomide exposure and during the second cycle and/or any subsequent cycle in which the dose of lenalidomide has been escalated. CBC should be checked weekly during any subsequent cycle in which the dose of lenalidomide has been reduced for hematologic toxicity.
- n. Response is assessed clinically (CBC, physical examination) after every 2 cycles of lenalidomide treatment beginning with Cycle 3 (Arm A) or Cycle 5 (Arm B), respectively. For patients meeting clinical criteria for CR for  $\geq$  2 months, bone marrow biopsy and CT scans should be performed to confirm response.
- o. The End of Therapy visit is defined as that occurring after 24 cycles. Patients discontinuing treatment at other times secondary to toxicity, progression, or preference only need the clinical assessment (except informed consent and education and counseling) and a complete blood count. Patients discontinuing for any reason are followed for at least 30 days to ensure resolution of any adverse events; however, these patients will still be followed for outcome until meeting criteria outlined in footnote "p" below.
- p. Patients no longer receiving active treatment are followed every 3 months during the first year and every 6 months thereafter until the patient receives a new CLL therapy, withdrawal of consent, or death.
- q. Unless completed within the last month.
- r. CT scans of the chest, abdomen, and pelvis.

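### After the first year off treatment the visit schedule falls short of the three-monthly infection recording in Section 6.3.10, and the Arm B calendar appears to omit four Follow-Up rows that Arm A marks

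*Combined protocol and SAP*

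**What the plan says.** Section 6.3.10 treats infection as a secondary endpoint and asks for it to be recorded and graded in a standard way "both during treatment and at least every three months following completion of protocol therapy for patients remaining on study". It sets no end date and draws no distinction between arms.

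Section 5.4 says of those who have stopped treatment that they "will continue to be evaluated at 3 month intervals for the first year and every 6 months thereafter". This ends only when another CLL treatment begins, consent is withdrawn or the patient dies, and progression alone need not end it. Footnote p of the Section 10 calendar gives the same pattern: "Patients no longer receiving active treatment are followed every 3 months during the first year and every 6 months thereafter". Section 10 adds: "Follow-Up visits have a +/- 14 day visit window".

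The content of those visits is left to the calendar. The Section 5.4 sentence that opens "Required historical, laboratory, and physical examination procedures at each follow-up visit are detailed in the" goes on to name the Section 10 calendar. Footnote n describes how response is judged: "Response is assessed clinically (CBC, physical examination) after every 2 cycles of lenalidomide treatment".

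Objective 1.2.3 is the incidence of infection and of invasive pneumococcal infection after concurrent or sequential treatment. Section 13.5 relies on follow-up after discontinuation to date subsequent treatment and progression. Section 11.5 defines progression partly by nodal, liver and spleen findings.

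**The concern.** There are two separate problems. The first lies in the running text and does not depend on any table: one section sets a recording interval that the visit schedule stops supporting after a year. Sites would have to choose which to follow, and nothing makes them choose alike.

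The second is a possible difference between the arms. Because Section 5.4 makes the calendar the list of follow-up procedures, a blank cell can be read as a procedure that is not required. In Arm B the row "Interval infection history" and three others appear blank at Follow-Up, while Arm A marks them. Adverse-event recording is blank at Follow-Up in both arms, so the infection-history row is the calendar's only dedicated line for infections off treatment. If the arms were followed differently, the arm examined and questioned less would tend to show fewer infections and less nodal or splenic progression. Later analysis cannot recover what was not collected.

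**Working it through.** The plan states no figure here to reproduce. The check is a visit count followed by a reading of the calendar cells.

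**Interval.** Inputs: recording at least every 3 months, so 4 a year (6.3.10); visits every 3 months in year 1, so 4, then every 6 months, so 2 a year (5.4, footnote p). For y whole years off treatment, recordings needed = 4y and visits scheduled = 4 + 2(y − 1).

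| Years off treatment | Needed, 4y | Scheduled, 4 + 2(y − 1) | Without a visit |
|---|---|---|---|
| 1 | 4 | 4 | 0 |
| 2 | 8 | 6 | 2 |
| 3 | 12 | 8 | 4 |
| 5 | 20 | 12 | 8 |

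The two rules agree in year 1. They then diverge by 4 − 2 = 2 a year, equally in both arms. The visit window does not close the gap. Taking six months as 182 days, an early visit after a late one is still 182 − 2 × 14 = 154 days later, against about 91 days for three months. The calendar schedules no interim contact.

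**Follow-Up column.** Each calendar has 12 columns after the procedure name, the last two being End of Therapy and Follow-Up. The Follow-Up cells read:

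| Row | Arm A | Arm B |
|---|---|---|
| Physical examination | marked | blank |
| Performance status | marked | blank |
| Concomitant medications | marked | blank |
| Interval infection history | marked | blank |
| Response assessment | marked | marked |
| Complete blood count | marked | marked |
| Adverse events | blank | blank |

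Arm B contradicts itself without any comparison with Arm A: it keeps response assessment at Follow-Up but not the examination that footnote n names as part of it.

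**Reliability of those cells.** Footnote h places the marrow at end of treatment. In Arm A the marrow mark falls under Follow-Up with End of Therapy blank; in Arm B it falls under End of Therapy. TSH shows the same one-column offset, and serum chemistries are marked at Follow-Up only in Arm A and at End of Therapy only in Arm B. Some cells have therefore probably moved in conversion. A sideways shift does not explain the four rows at issue. Arm A's examination row has 12 marks and Arm B's has 11; infection history has 11 and 10. The complete blood count row in the same Arm B table fills all 12. A mark lost from four adjacent rows would explain it, and the converted text cannot rule that out.

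**The case against.** The strongest reply is that the arm difference rests on the last columns of converted tables that show visible displacement, while the arm-neutral text already requires the data. Section 6.3.10 covers every patient remaining on study, Section 5.4 refers to history and examination at follow-up visits without naming an arm, and footnote n brings an examination into Arm B's response assessment. This largely stands. A reader might infer that Arm B is designed to have no infection histories or examinations off treatment. The documents do not support that: at most, Arm B's calendar disagrees with text that requires them.

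A reader might also see an end-of-therapy CT in Arm B with none in Arm A. That rests on the End of Therapy column in which Arm A's marrow, TSH and chemistry marks are also missing, so no difference in imaging should be concluded.

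On the interval, one might say that the three-month frequency is impossible to meet. That goes too far. Footnote p sets visits and does not forbid other contacts, and a history covering the time since the last visit can pick up earlier infections. What remains is an unscheduled requirement and a longer recall period, the same in both arms.

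The impact is also limited. Infection history is marked in every treatment cycle in both arms. Twenty-four 28-day cycles are 24 × 28 = 672 days, about 22 months, so for patients who complete therapy little of the two-year progression-free window is off treatment. Section 13.5 plans no formal between-arm comparison of time-to-event outcomes and sets out no between-arm test for infection.

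**Conclusion.** The concern holds in two parts of different strength. The interval conflict is certain from the running text: from the second off-treatment year, two of four required recordings a year have no scheduled visit, in both arms. This assumes that remaining on study, which the protocol does not define, includes the follow-up phase of Section 5.4.

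The Arm B omission is probable rather than proven and depends on the original page. If the blanks are real and sites followed them literally, off-treatment infection and examination-based progression could be under-ascertained in Arm B, making that arm look better in descriptive summaries. The documents give no off-treatment infection rate, so the size of such a bias cannot be calculated. The primary antibody comparison, made one month after the second vaccination, is not touched. This should be corrected, but it does not threaten the trial's main conclusion.

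**What to change.** 1. Reconcile Section 6.3.10 with Section 5.4 and footnote p so that one infection-recording interval applies after therapy. If recordings are to be more frequent than visits, say how they are obtained.
2. Check the End of Therapy and Follow-Up columns of both calendars against the original page. Mark physical examination, performance status, concomitant medications and interval infection history at Follow-Up in both arms.
3. Before summarising infections by arm, establish what was actually collected in Arm B after treatment. Report infections over follow-up time ascertained in the same way in both arms, for instance as events per patient-year. If the off-treatment data differ by arm, limit the comparison to the period with common collection and say so.

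The cost is a calendar and wording correction plus slightly more data entry in Arm B follow-up, at visits that already take place. If the three-month interval is kept, it adds 4 − 2 = 2 interim contacts per patient-year from the second off-treatment year, in both arms.
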